11.2 Definitions of Analysis Variables

Formal definitions of variables used in analyses can be found in the Statistical Considerations section of the protocol.

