The following thresholds will be used to summarize lifestyle measures at baseline and at 2 years, and to define patient subgroups for evaluating differential treatment effects: Body mass index (BMI) categories will be defined according to the World Health Organization as underweight ($<18.5 \text{ kg/m}^2$) or normal weight ($18.5\text{-}24.9 \text{ kg/m}^2$) versus overweight ($25\text{-}29.9 \text{ kg/m}^2$) or obese ($\text{BMI} \geq 30 \text{ kg/m}^2$). The anticipated prevalence of overweight (30%) and obese (36.5%) patients are taken from Centers for Disease Control and Prevention report for US Women age 20 years or older [24]. Physical activity categories by a modified Paffenbarger questionnaire will be defined as sedentary ($< 3 \text{ METs}$, 32% prevalence) versus CDC recommended ($3\text{-}8.9 \text{ METs}$, 29% prevalence) or active ($\geq 9 \text{ METs}$, 39% prevalence) [25]. Sleep will be assessed with the Pittsburgh Sleep Quality Index (PSQI) with scores ranging from 0 to 21 and poor quality sleep defined as great than 5 [26]. The mean PSQI was 5.5 and 6.7 in cohorts of middle age white and black women, respectively [27]. A median PSQI of 9 was reported in early stage breast cancer patients with aromatase inhibitor induced musculoskeletal symptoms [28]. Depression will be assessed by the Center for Epidemiologic Studies-Depression scale-Revised (CESD-R) with scores ranging from 0 to 6 and possible depression defined as ≥ 16 [29, 30]. Median CESD-R as 10.5 in early stage breast cancer patients with aromatase inhibitor induced musculoskeletal symptoms [28]. The Perceived Stress Scale (PSS) will be assessed using the 10 item scale (PSS-10) with scores less than 16 defining "normal" for breast cancer patients [31] with a prevalence of 61% in early stage breast cancer patients 12 months after initiation of chemotherapy [32]. Secondary and exploratory analysis will evaluate the lifestyle measures listed above as continuous factors and will evaluate individual items from the Brief Pain Inventory (BPI) dichotomized at ≥ 4 on the 0-10 Likert scales [33]. Pain had a reported prevalence of 21% in early stage breast cancer patients taking aromatase inhibitors [34].

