14.1.3.3 Sleep assessment

Sleep will be assessed with the Pittsburgh Sleep Quality Index (PSQI). The PSQI is a self-administered 19-item questionnaire used to measure the quality and patterns of sleep in adults. It differentiates "poor" from "good" sleep by measuring seven areas: subjective sleep quality, sleep latency, sleep duration, habitual sleep efficiency, sleep disturbances, use of sleeping medication, and daytime dysfunction during the last month. Scoring is based on a 0 to 3 scale, where a score of 3 reflects the negative extreme on the Likert Scale. A global score of five or greater indicates a "poor" sleeper [26].

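### Do the two PSQI cuts and the impossible CESD-R range leave the lifestyle subgroups undefined?

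*Combined protocol and SAP*

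**What the plan says.** Objective 2.2.5 asks whether patients with more inflammatory lifestyle profiles gain more from aspirin. Section 13.5 lists the thresholds that will summarise the lifestyle measures at baseline and 2 years and define the subgroups. The dichotomised factors then enter Cox models for iDFS and OS as treatment interactions, tested jointly by one likelihood ratio test at alpha 0.05.

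- **PSQI.** Section 13.5 gives a range of 0 to 21 and "poor quality sleep defined as great than 5". Section 14.1.3.3 says "A global score of five or greater indicates a" poor sleeper. Both cite reference 26.
- **CESD-R.** Section 13.5 describes the scale "with scores ranging from 0 to 6 and possible depression defined as" 16 or more, then reports "Median CESD-R as 10.5 in early stage breast cancer patients" with joint symptoms on an aromatase inhibitor. Section 14.1.3.4 describes a 20-item form and uses the same cut of 16.
- **Continuous use.** Secondary and exploratory work "will evaluate the lifestyle measures listed above as continuous factors".
- **Which section governs.** Section 11.2 states: "Formal definitions of variables used in analyses can be found in the Statistical Considerations section of the protocol".

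**The concern.** A subgroup analysis depends on its cut-points. If two sections give different PSQI cuts, an analyst could in principle choose between them. Section 13.5 schedules this work after the primary comparison, when treatment results are known. The boundary also falls where scores may be dense: Section 13.5 reports that "The mean PSQI was 5.5 and 6.7 in cohorts of middle age white and black women, respectively".

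The CESD-R text looks worse. On a 0 to 6 scale nobody reaches 16, so the depressed subgroup would be empty and the quoted median impossible. The likely repair, a lost digit giving 0 to 60, raises a further question. The Appendix I form prints five response columns coded 0 to 4, and twenty such items sum to 80, not 60. How the fifth column is scored would change the continuous score of anyone who used it, and could move a few borderline patients across the cut.

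**Working it through.** **1. The plan's own power figures.** Section 13.5 assumes 216 placebo and 165 aspirin events and 80% power. With two-sided alpha 0.05 and prevalence p,

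ratio of HRs = exp[ −(1.960 + 0.842) × √{(1/216 + 1/165) × (1/p + 1/(1−p))} ].

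At p = 0.50, (0.004630 + 0.006061) × 4 = 0.04276; its square root is 0.2068; times 2.802 gives 0.579; exp(−0.579) = 0.560. At 40, 30 and 20% the results are 0.554, 0.531 and 0.485. The printed table reads 0.56, 0.55, 0.53 and 0.48, so it is reproduced. Its inputs are event counts and nominal prevalences, so neither slip affects it.

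**2. Where the PSQI rules differ.** Of the integers 0 to 21, only 5 is classified differently.

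**3. How many patients that is.** The documents give centres of 5.5 and 6.7, and "A median PSQI of 9 was reported in early stage breast cancer patients" with joint symptoms. They give no SD. Assume an SD of 2.5 to 4 and a normal distribution rounded to integers and truncated to 0-21.

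| Centre | Share scoring 5 | Poor sleepers, >5 | Poor sleepers, ≥5 | Detectable ratio, >5 | Detectable ratio, ≥5 |
|---|---|---|---|---|---|
| 5.5 | 10.6-15.7% | 50-54% | 64-66% | 0.56 | 0.54-0.55 |
| 6.7 | 9.4-12.6% | 64-69% | 74-81% | 0.54-0.55 | 0.48-0.52 |
| 9 | 4.5-6.1% | 82-92% | 88-96% | 0.35-0.47 | 0.21-0.41 |

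If all 2936 patients answered, about 130 to 460 would score exactly 5. In every row the Section 13.5 cut gives the more even split and the detectable ratio closer to 1, so moving to the Section 14.1.3.3 wording would gain nothing.

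**4. Which PSQI rule governs.** Section 13.5 says its thresholds will be used to form the subgroups. Section 14.1.3.3 describes the questionnaire within the companion-study text and assigns no analysis role to its figure. Section 11.2 points to Section 13. Followed as written, the plan uses above 5.

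**5. CESD-R range.** None of the seven values 0 to 6 reaches 16, and 10.5 exceeds 6, so the printed range is the faulty element. The cut agrees in both places where it appears. No formula, model or table uses the maximum score.

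**6. CESD-R item scoring.** Twenty items scored 0-3 reach 20 × 3 = 60; scored 0-4 they reach 20 × 4 = 80. Let C be the total with the fifth column scored 3, and k the number of fifth-column answers, so that summing the printed codes gives C + k. The two scorings disagree at 16 only when C ≤ 15, C + k ≥ 16 and C ≥ 3k. That leaves C = 12 with k = 4; C = 13 with k = 3-4; C = 14 with k = 2-4; and C = 15 with k = 1-5: 1 + 2 + 3 + 5 = 11 combinations. The continuous score shifts by one point per fifth-column answer. Both scorings are assumptions, and the documents give no item distribution, so the share affected cannot be estimated.

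**The case for a change.** The best argument for acting is that correction is cheap and the timing matters: a few words would fix both sections before anyone sees results by arm. The scoring point also has some substance. The Perceived Stress Scale in the same appendix is coded 0-4, and its ten items give 10 × 4 = 40, the stated range. A reader could therefore expect the CESD-R codes to be summed as printed. The Section 6.2 table calls the instrument CES-D while Sections 13.5 and 14.1.3.4 and the form say CESD-R. By title, reference 29 concerns the CES-D and reference 30 covers both.

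What stands is that the wording is untidy and the fifth-column scoring is not written out. It does not follow that an analysis choice is open. The PSQI cut is settled by the order of the sections. The CESD-R cut is stated consistently and cites two references, whose scoring instructions cannot be seen here and may well answer the question. The evidence for a scoring conflict is a flattened table with codes on one row, which may be response labels rather than weights. The missing digit may itself have been lost when the PDF was read. Asking how the fifth column is scored is a fair query to the study team, but no effect on a result has been shown.

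**Conclusion.** No change to the plan is needed. The PSQI mismatch is a clerical difference between an instrument description and the governing analysis section; the plan as written uses above 5. The CESD-R range is a misprint or an extraction loss beside a cut that agrees wherever it is stated. The unstated item scoring is a detail that analysts can take from the instrument's scoring rules.

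The reach is limited to the lifestyle summaries at baseline and 2 years and the iDFS and OS interaction models, all run after the primary analysis. Using the wrong PSQI wording would reclassify about 9-16% of patients at means of 5.5 to 6.7, or 4.5-6% centred on 9. Those shares rest on the assumed SD of 2.5 to 4, an approximately normal shape, and centres taken from other populations. The primary iDFS test, the 381 events, the futility rules and the interaction power table are unaffected. If the text is opened for another reason, aligning Section 14.1.3.3 with Section 13.5 and checking the CESD-R range against the source file would be reasonable housekeeping.

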2.2 Secondary Objectives

2.2.1 To compare the effect of aspirin versus placebo in early stage HER2 negative breast cancer patients upon:

- a) Distant disease-free survival
- b) Overall survival
- c) Cardiovascular disease (see [Section11.3](#))

2.2.2 To compare the toxicity of aspirin versus placebo in early stage HER2 negative breast cancer patients.

2.2.3 To assess adherence to aspirin and placebo among early stage HER2 negative breast cancer patients.

2.2.4 To bank tumor and germline deoxyribonucleic acid (DNA), plasma and urine collected at baseline and sequential plasma and urine collected 2 years later for future measurement of inflammatory markers.

2.2.5 To determine if there are subgroups of participants characterized by lifestyle factors associates with greater inflammation for whom there is greater benefit of aspirin versus placebo upon iDFS.

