13.3.3 Analysis plans for primary and secondary endpoints

The primary analyses of iDFS will be performed in an intention-to-treat manner, in which all patients including those who do not begin protocol therapy will be analyzed according to their assigned arm. The primary determination of efficacy will be a time-to-event analysis using the Kaplan-Meier method for estimation, and the stratified log-rank test of iDFS to compare the aspirin arm versus the placebo arm (with stratum defined by hormone receptor status, BMI and stage), using the nominal alpha defined by the group sequential design, as given in [Section 13.4.2](#). A secondary analysis to estimate efficacy will use a multivariate Cox proportional hazard model to evaluate differences between arms after adjusting for stratification factors and the additional covariates of known importance to breast cancer including age, tumor size, and number of involved nodes. Identical models will be used to evaluate differences between arms in DDFS and OS.

Planned subgroup analyses will evaluate the hazard ratio of aspirin to placebo in subgroups defined by the study stratifiers of hormone-receptor status and enrollment time (HR positive and enrolled \leq 18 months from time from diagnosis vs HR positive and enrolled $>$ 18 months from diagnosis vs HR negative) and body-mass index (less than 30 kg/m^2 vs at least 30 kg/m^2). In addition to the WHO thresholds for underweight ($<18.5 \text{ kg/m}^2$), normal weight ($18.5\text{-}24.9 \text{ kg/m}^2$), overweight ($25\text{-}29.9 \text{ kg/m}^2$) and obese ($\text{BMI} \geq 30 \text{ kg/m}^2$), we will explore a linear association in the multivariate Cox model, based on the findings of Ligibel et al. that the prognostic relationship to disease-free survival with adjuvant chemotherapy was linear across the entire range of BMI observed at baseline. Further, an exploratory analysis will evaluate whether baseline factors are predictive of difference in clinical benefit of aspirin over placebo using multiplicative interactions in the Cox model. All tests of secondary objectives will use a two-sided Type I alpha of 0.05, and point estimates will be reported with 95% confidence intervals taken from Cox models.

Analyses of toxicity will be conducted on patients who receive at least one dose of aspirin or placebo. Toxicity will be reported by type and maximum grade using CTCAE v4.03 and contrasts of aspirin to placebo will use Fisher exact tests.

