The hypothesis is that subgroups of participants, defined by lifestyle factors that are potential pro-inflammatory states, would receive greater treatment benefit from aspirin. The potential for any baseline state to modify the effect of treatment upon iDFS and OS will be evaluated using multivariate Cox proportional hazards models that include study stratification factors main effects and pairwise interaction between each dichotomous baseline factor and treatment arm. Simultaneous testing of the lifestyle factors will be performed, using a single likelihood ratio test (LRT) of a "full" model with all terms versus a "reduced" model with only main effects for treatment assignment, study stratification factors, and lifestyle factors. The LRT for the multivariable Cox regression model will use an alpha = 0.05. If the "full" model is found to be superior under the LRT, a stepwise backward-selection process will be used to identify the set of individual factors with the strongest interaction with treatment assignment, using a nominal

$p < 0.05$ for inclusion in the final model. The following table proves the effect sizes there will be 80% power to detect using the method of [35] for a marginal bivariable test with time-to-event data. Effect sizes are calculated for varying prevalences of pro-inflammatory states, assuming a quantitative interaction and final analysis occurs when 381 IDFS events (216 events in the placebo arm and 165 events in the aspirin arm).

Prevalence	Ratio of HRs
50%	0.56
40%	0.55
30%	0.53
20%	0.48

Association of measures of inflammatory states, factors or markers at 2-years with clinical outcome will be explored using landmark analyses of IDFS and OS in the subset of patients that are evaluable and event-free. All adjusted HRs and ratios of HRs from the final multivariable models will be reported with 95% confidence intervals. Hypothesis tests of inflammatory markers from banked biospecimen will be exploratory and hypothesis-generating using a nominal two-sided alpha = 0.05 for each analyte, and estimates of the false discovery rate (FDR) for multiple inflammatory markers that are potentially correlated will be obtained using the resampling-based Yekutieli-Benjamini method [36].

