14.1.1 Background

There are several possible mechanisms for aspirin decreasing the risk of cancer recurrence with inflammation being one of them. We hypothesize that the effect of aspirin may be strongest in those participants who have lifestyle factors associated with inflammation. The lifestyle factors we have chosen to assess are body mass index, physical activity, sleep quality, depression, perceived stress, and pain for the reasons detailed below.

Many obese individuals develop a chronic low-grade inflammatory state that can possibly be assessed histologically and biochemically. Their enlarged adipocytes show higher expression of pro-inflammatory proteins such as TNF α , IL-6 and to recruit macrophages, all of which correlate with insulin resistance [37, 38]. Simpson and Brown recently reviewed the role of inflammation and aromatase in obesity-related breast cancer [39]. The adipocytes in the breasts of obese women have been shown sometimes to be surrounded by macrophages forming crown-like structures and to have correlated increased aromatase activity as a consequence of increased generation of pro-inflammatory mediators [39-41]. Mouse models have shown that obesity increases tumor associated macrophage infiltration [42]. Physical activity of course ameliorates obesity and is of itself associated with lower markers of inflammation [43].

Stress-related changes in the hypothalamic-pituitary-adrenal (HPA) and the sympathetic nervous system (SNS) have been associated with low-grade inflammation by increasing systemic C-reactive protein (CRP) and IL-6 levels. Neuroendocrine stress pathways lead to increased secretion of epinephrine and norepinephrine has been shown to suppress cellular immunity, particularly NK cells. These stress pathways promote angiogenesis via proangiogenic cytokines VEGF and IL-6, and facilitate migration and invasion of tumor cells by inducing production of matrix metalloproteinases (MMP).

One interesting consideration is that these relationships could be bidirectional; an increased tumor inflammatory response could lead to increased subjective experience of depression and stress [38]. Chronic pain and depression frequently co-occur, and are thought to be linked by inflammation as the common mediator [44]. Sleep disturbances are common in those with chronic pain and in those with depression; experimental studies in healthy humans have shown that both prolonged and moderate sleep loss increase mediators of inflammation [45].

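### Section 13.5 leaves age, tumor size and involved nodes out of its Cox models: the interaction test for objective 2.2.5 stands, but lifestyle main-effect and 2-year landmark hazard ratios can carry residual confounding

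*Combined protocol and SAP*

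**What the plan says.** Objective 2.2.5 (Section 2.2) asks whether there are "subgroups of participants characterized by lifestyle factors associates with greater inflammation for whom there is greater benefit of aspirin versus placebo upon iDFS". Section 13.5 addresses it with "multivariate Cox proportional hazards models that include study stratification factors main effects and pairwise interaction between each dichotomous baseline factor and treatment arm". One likelihood ratio test at alpha 0.05 sets this full model against a reduced model "with only main effects for treatment assignment, study stratification factors, and lifestyle factors". If the full model is better, backward selection looks for the factors that interact most strongly with treatment. Power is tabulated as a detectable ratio of hazard ratios.

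On output, Section 13.5 states: "All adjusted HRs and ratios of HRs from the final multivariable models will be reported with 95% confidence intervals". It also plans a second kind of analysis: "Association of measures of inflammatory states, factors or markers at 2-years with clinical outcome will be explored using landmark analyses of IDFS and OS". No covariates are named for it.

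Section 13.3.3 describes the secondary Cox model for iDFS, repeated for DDFS and OS. It adjusts for the stratification factors and for "the additional covariates of known importance to breast cancer including age, tumor size, and number of involved nodes".

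**The concern.** The plan uses two covariate sets for iDFS and OS and gives no reason for the smaller one. For BMI the overlap is direct. Section 13.3.3 explores BMI as a linear term in its multivariate Cox model, while Section 13.5 treats BMI as one of the lifestyle factors. The plan could thus report two differently adjusted results for one factor and one outcome.

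Activity, sleep, depression, stress and pain are not randomised. If age, tumor size or nodal burden is related to them and also to recurrence, a factor with no effect of its own can look prognostic. Section 14.1.1 raises a related possibility itself: "an increased tumor inflammatory response could lead to increased subjective experience of depression and stress". At stake is how far the published lifestyle hazard ratios and 2-year associations can be read as being about inflammation rather than about age and disease burden.

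**Working it through.** **1. The plan's own figure.** Inputs from Section 13.5: 216 placebo and 165 aspirin events, 80% power, alpha 0.05 (taken as two-sided), prevalence p.

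Detectable ratio of HRs = exp(−(1.960 + 0.842) × √[(1/216 + 1/165) × (1/p + 1/(1−p))]), with 1/216 + 1/165 = 0.01069.

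| p | variance | computed | stated |
|---|---|---|---|
| 50% | 0.0428 | 0.560 | 0.56 |
| 40% | 0.0445 | 0.554 | 0.55 |
| 30% | 0.0509 | 0.532 | 0.53 |
| 20% | 0.0668 | 0.485 | 0.48 |

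The table reproduces. The planned test is of the interaction and its power statement is sound.

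**2. Does the omission touch the interaction?** Trials of 2936 patients were simulated, 600 per scenario. The Cox model held treatment, stage, lifestyle and their interaction, with and without a disease-extent factor U beyond stage. Assumed, because the documents give no values: odds ratio of lifestyle with U, and hazard ratio of U. There was no true lifestyle effect or interaction. The runs had 475, 475 and 591 events on average, more than the planned 381.

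| OR, HR of U | ratio of HRs, U omitted / included | rejection, omitted / included | lifestyle HR in placebo arm, omitted / included |
|---|---|---|---|
| 1.5, 2 | 0.994 / 0.995 | 4.5% / 4.8% | 1.06 / 1.00 |
| 3, 2 | 1.003 / 1.002 | 5.8% / 5.8% | 1.18 / 1.00 |
| 3, 3 | 1.013 / 1.014 | 5.0% / 4.8% | 1.28 / 1.00 |

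The ratio of HRs moves by at most 0.001. Only the lifestyle main effect moves.

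**3. Size for a main effect at 381 events.** Take a lifestyle factor with prevalence 39% (what the 61% prevalence of normal perceived stress in Section 13.5 leaves) and no true effect. Cut it from a normal score with correlation ρ to a normal prognostic index of SD σ on the log-hazard scale. Both ρ and σ are assumptions.

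Mean index difference between patients with and without the factor ≈ ρσ × φ(0.279)/(0.39 × 0.61) = ρσ × 0.3837/0.2379 = 1.613ρσ.

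SE of the log HR ≈ 1/√(381 × 0.39 × 0.61) = 0.105.

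| ρ | σ | spurious HR = exp(1.613ρσ) | two-sided 5% rejection | simulated HR, rejection |
|---|---|---|---|---|
| 0.1 | 0.3 | 1.05 | 7% | 1.05, 8% |
| 0.1 | 0.5 | 1.08 | 12% | 1.09, 13% |
| 0.1 | 0.7 | 1.12 | 19% | 1.11, 17% |
| 0.2 | 0.3 | 1.10 | 15% | 1.10, 14% |
| 0.2 | 0.5 | 1.17 | 34% | 1.17, 34% |
| 0.2 | 0.7 | 1.25 | 57% | 1.24, 53% |

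The simulated column has 2000 runs per cell and no stage term. At ρ = 0.05 its rejection rate was 6–9%. With the index in the model, the HR was 1.00 and rejection 4–6% throughout.

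**4. Does stage remove it?** A further simulation kept a stage term in the model, with the same ranges of σ (0.3–0.7) and ρ (0.1–0.2). The null lifestyle HR was 1.05–1.25 with 7–56% false significance unadjusted, against about 1.00 and 2–6% adjusted.

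**5. Effect of the change on the interaction's power.** With stage in the model, the change was about −0.3 to +1.8 points. Without stage, at a ratio of HRs of 0.55, it was +0.6, +1.4 and +2.6 points for σ = 0.3, 0.5 and 0.7.

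**The case against.** The strongest reply is that objective 2.2.5, the hypothesis in Section 13.5 and the objective in Section 14.1.2 all ask about differential benefit of aspirin. No objective asks for a prognostic lifestyle hazard ratio. The likelihood ratio test and the backward selection concern interactions only, so the false-significance rates above belong to a test that the plan does not schedule. This stands. A reader might infer from the missing covariates that the objective 2.2.5 result is confounded; randomisation within lifestyle subgroups and step 2 show that it is not. The main-effect rates are best read as how often a reported 95% interval would exclude 1.

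Second, the adjusted HRs to be reported may mean aspirin HRs within subgroups. That reading is possible, but the text does not restrict it, and the final models contain lifestyle main effects.

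Third, disease extent is partly in the model through stage, and the lifestyle factors adjust for one another. This stands in part: size and node count vary within a stage stratum, age is absent, and Section 13.3.3 itself adds all three on top of the strata.

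Fourth, the landmark analyses are exploratory, and leaving covariates unnamed does not exclude them. Markers from banked samples will get their own statistical section before testing (Section 15.1). Both points stand. They lower the priority, but the questionnaire-based landmark models remain unspecified.

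Fifth, Section 13.3.3 already plans exploratory interactions in the Cox model, arguably the adjusted one. That concerns interactions and leaves main effects and landmark associations as they are.

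Finally, Section 14.1.1 speaks of a tumor inflammatory response that could affect depression and stress. A reader might infer that the protocol links age, tumor size or nodes to lifestyle; it does not.

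**Conclusion.** The interaction test for objective 2.2.5 is valid as written. What remains is narrower: lifestyle main-effect HRs from the 13.5 models, if reported, and the 2-year landmark associations can carry residual confounding by age and by disease extent beyond stage I/II versus III.

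The documents do not show that these estimates are confounded, or by how much. The illustrative HR of 1.05–1.25 for a null factor rests wholly on the assumed SD of 0.3–0.7 and correlation of 0.1–0.2; a weaker correlation gives little bias. The rejection rates assume 381 events. A landmark analysis starts after 2 years in event-free patients and will have fewer, so its intervals will be wider and its rejection rates lower for the same bias.

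A reader might also infer that adding the covariates would make a lifestyle interaction causal. It would not. When disease extent itself modified the aspirin effect (assumed ratio 0.6), the lifestyle ratio of HRs was 0.862 without its main effect and 0.861 with it.

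This is a free improvement. Its priority is modest because the analyses are secondary or exploratory.

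**What to change.** In Section 13.5, add main effects for age, tumor size and number of involved nodes to both the full and the reduced model, and keep them in throughout backward selection. For the 2-year landmark models of iDFS and OS, name the covariates: the same three, the stratification factors and treatment arm.

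The cost is a sentence or two of wording. The covariates are already planned for Section 13.3.3. With one linear term each, they add three parameters to a model with 381 events. Because they enter both models, the degrees of freedom of the likelihood ratio test do not change. The gain in interaction power is a point or two at most once stage is in the model, and is not the reason to make the change.
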